## 9.4: Interim Analyses and Stopping Rules

### 9.4.1: Study-wide stopping rules

These include the occurrence of a serious adverse event, CTCAE Grade 3 or higher, possibly related to the study protocol, occurring in 5 or more randomized adolescents. If these conditions occur, the ISMC will review and make recommendations on the advisability of continuing the study

### 9.4.2: Individual stopping rules

If a participant scores above 12 on the combined parent and child SMFQ at any point in the study, s/he will be referred to the study psychologist ([name]) within 24 hours. The study psychologist will then contact the parent of the teen (within 24 hours) to inform the parent of the depression status of the teen. [name] will make an evaluation to determine if s/he can continue in the study and will refer the family for appropriate psychological care.

We have added a safety depression screening measure, the PROMIS pediatric depression scale, which will be administered weekly via REDCap. The Assessment Center at NIH provides a scoring algorithm with REDCap software, enabling use of the measure for safety monitoring. The Project Manager or trained designee will monitor these measures weekly and will alert the team (including the Study Psychologist) to sharp increases in depressive symptoms and depressive symptoms meeting criteria for major depression. If the Study Psychologist confirms the development of major depression, the adolescent will be withdrawn from the study and referred for further care.

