### 7.1: Specification of Safety Parameters

Combined SMFQ-C / SMFQ-P scores of 12 is the recommended cut-off value for MDD; this value or greater will generate follow-up with the study psychologist. In addition, a T score of 70 or an increase of 3 standard deviations from the baseline score on the PROMIS depression measure will generate a referral to the study psychologist.

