### 7.5: Follow-up for Adverse Events

The Study Psychologist will investigate AEs related to participant mental health and make appropriate referrals for further care. The Study Psychologist will follow-up with the parent to assess follow-through within one week of the reported event. The Project Manager will investigate all other AEs and follow up with the participant until stable.

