### 9.4.3: Additional Reasons for Withdrawal of a Participant

Additional reasons a participant may withdraw from the study include:

- The adolescent wishes to withdraw from the study;
- Loss of study eligibility (development of major depression);
- Intervening illness or injury making participation difficult;
- The adolescent develops any condition that, in the opinion of the study psychologist, would make continued participation unsafe.

In the unlikely event that a participant is unable to participate in a group setting, s/he may be withdrawn from the study.

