##### 6 EXPECTED RISKS

Expected risks to the subject are as follows:

- **Risk of depression.** The study population, adolescents aged 14 through 18, is considered at risk for developing MDD based on their baseline **subsyndromal** depression (6 or higher on QIDS). It is unknown whether the study itself may contribute directly to the development of MDD in the participants. Since development of MDD is a risk based on the selection criteria for participation, staff will be trained by the project psychologist in the detection of worsening depressive symptoms and reporting of same to the PI for intervention if necessary. Monitoring will also take place with a) the PROMIS Pediatric Depression Short Form (weekly) and b) the short Mood and Feelings Questionnaire (SMFQ-C and SMFQ-P), completed by both the adolescent and a parent before and after the intervention, and 3, 6 months after the intervention. Adolescents will be asked to complete the PROMIS Pediatric Depression Measure through a survey interface on REDCap that provides immediate scoring. The project manager will monitor the PROMIS Depression short form scores weekly and scores on the Mood and Feelings Questionnaire (MFQ) after each administration. A T score of 70 or

greater on the PROMIS Depression short form or a combined child and parent score of 12 or greater on the MFQ will trigger an evaluation by the Study Psychologist.

- Participants will be encouraged to report any change in health status, including mood, to research personnel, instructors, and parents. Reports of increasing depressive symptoms will be reviewed by the Study Psychologist for consideration of appropriate action, including 1) direct confrontation, 2) informing parents, 3) referral to outpatient health care resources in the community, and 4) escorting the participant to emergency facilities for psychological assessment and treatment. Documentation of these events will be reported to the IRB and entered into the case report form for review by the Independent Safety Monitoring Committee (ISMC).

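### At a combined SMFQ score of exactly 12, the protocol's own MDD cut-off, psychologist follow-up is required but the 24-hour referral and parent-contact limits do not apply

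*Combined protocol and SAP*

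**What the plan says.** Four places in current text set an action on the combined SMFQ score.

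- Protocol 7.1 states the cut-off and the action together: "Combined SMFQ-C / SMFQ-P scores of 12 is the recommended cut-off value for MDD; this value or greater will generate follow-up" with the study psychologist. It gives no time limit.
- DSMP, Expected Risks: a "combined child and parent score of 12 or greater on the MFQ will trigger an evaluation by the Study Psychologist". The same section has the project manager review "scores on the Mood and Feelings Questionnaire (MFQ) after each administration", again with no time limit for acting on a score. It writes MFQ, but introduces the measure as the short form in child and parent versions, so the instrument is the same.
- Protocol 9.4.2: "If a participant scores above 12 on the combined parent and child SMFQ at any point in the study", referral to the study psychologist follows within 24 hours. Next, "The study psychologist will then contact the parent of the teen (within 24 hours"). The psychologist then judges whether the teen can continue.
- DSMP 7.3 repeats the 9.4.2 rule with the same threshold wording and the same two limits.

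Withdrawal is handled separately. Protocol 9.4.2, in its paragraph on PROMIS monitoring, says "If the Study Psychologist confirms the development of major depression, the adolescent will be withdrawn from the study and referred for further care", and DSMP 7.3 agrees. Protocol 9.4.3 lists "Loss of study eligibility (development of major depression") as a reason for withdrawal without tying it to any instrument.

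**The concern.** The participants are minors selected because they are at risk of major depression, and the DSMP names suicide as a potential risk. The 24-hour limits exist to bring a possible case quickly to the psychologist and the parent. As written, they begin one point above the score that the protocol itself treats as the MDD cut-off. Staff who work from 9.4.2 have no deadline for a teen at 12, while staff who work from 7.1 know that the same teen must be followed up. Two people applying the plan correctly could handle the same score at different speeds. What is at stake is the timing of a safety response, not the analysis.

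**Working it through.** The plan states no figure to reproduce, so the check is a side-by-side reading.

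| Place | Threshold | Action | Time limit |
|---|---|---|---|
| Protocol 7.1 | 12 or more | psychologist follow-up | none |
| DSMP, Expected Risks | 12 or more | psychologist evaluation | none |
| Protocol 9.4.2 | more than 12 | referral; parent contact | 24 h; 24 h |
| DSMP 7.3 | more than 12 | referral; parent contact | 24 h; 24 h |

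Assume that the combined score is a whole number (the documents give no SMFQ scoring key). Then:

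- at 11 or less, none of the four rules applies;
- at 13 or more, all four apply, with the 24-hour limits (24 + 24 = 48 hours at most to parent contact, if the second limit runs from the referral);
- at 12, the first two apply and the last two do not, so the action is required but has no deadline tied to the score.

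The next step is to see whether another section supplies the missing deadline.

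- Section 3 has the psychologist contact parents when the SMFQ captures incident major depression, but gives neither a threshold nor a time.
- DSMP Expected Risks provides immediate referral for severe distress in class or for a marked rise or threshold score on PROMIS. That helps a teen who also meets one of those conditions, but it is not triggered by the SMFQ.
- Section 7.5 says "The Study Psychologist will follow-up with the parent to assess follow-through within one week of the reported event". This times a check on follow-through after a reported event. It does not time a first referral or a first parent contact, and no section says that a score of 12 is logged as an adverse event.
- Sections 9.4.2 and 9.4.3 and DSMP 7.3 govern withdrawal once MDD is present, and set no time to evaluation.

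No section therefore sets a deadline at exactly 12.

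For the number of occasions, the combined score needs both forms. Section 5.1.2 and Table 3 place the parent form at Visits 2, 10, 13 and 16, which gives four. The parent rows of Table 2 add Visit 6, which gives five. The schedule is inconsistent on this, so both counts are stated.

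**The case against.** The strongest reply is that the two thresholds do not contradict each other: both can be obeyed together, and a teen at 12 loses only a clock. That is right, and it is why the point is minor.

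It can also be said that other routes shorten the practical gap. PROMIS is reviewed weekly, a mental health provider assists each program and confers with the psychologist, instructors report concerns, and the psychologist is available at once to staff when self-harm is in question. These stand as mitigation. Any of them may prompt an early referral, but none sets a limit for an SMFQ score of 12.

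One might argue that the higher threshold for urgent handling is deliberate. Nothing in the documents describes 12 as a less urgent tier, and 7.1 puts it at the MDD cut-off, so a slip in wording is the more natural reading.

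Finally, section 9.5.1 of version 1.1 (March 2021) describes SMFQ collection in the past tense. This does not prove that collection had ended, but an edit may come too late to help anyone in this trial.

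A reader might infer more than the text supports in three ways:

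- That a teen at 12 goes unevaluated, or stays in the study with confirmed MDD. The follow-up, evaluation and withdrawal provisions rule this out.
- That the one week in 7.5 is what remains in place of the 24-hour limits. It times something else, and the other routes above exist.
- That the SD of 6 in DSMP 7.2 allows a count of teens at 12. No mean or distribution of the combined score is given, and the text does not say whether that SD is of scores or of change.

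**Conclusion.** The inconsistency holds, in current text of both the protocol and the DSMP, and it is minor. It covers one score value and concerns only how fast the psychologist and the parent are brought in. It rests on whole-number scoring and on taking both wordings literally. The number of teens affected cannot be derived from the documents. No endpoint, censoring rule or power figure depends on it; the time-to-event outcome uses the PROMIS T-score.

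**What to change.** In protocol 9.4.2 and DSMP 7.3, replace *above 12* with *12 or greater*, so that the time-limited rule starts at the cut-off in 7.1. The cost is a few more 24-hour referrals and parent contacts, for teens whose follow-up 7.1 already requires. Analysis, visit schedule and sample size stay as they are. If SMFQ collection was complete by version 1.1, the change protects no one in this trial, but it corrects the rule for the larger trial that this study is meant to inform.

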**Patient-Reported Outcomes Measurement Information System Pediatric Short Form (PROMIS Pediatric Short Form)**: The PROMIS Pediatric Short Form is a short 12-item survey designed to screen for depression. The PROMIS Pediatric Short Form will be used as a safety measure once participants are in the 8-week course to assess any changes in depressive symptoms. See [7. Safety Assessments](#) for more details about the PROMIS Pediatric Short Form being used as a safety measure for the study. A T score of 70 on the PROMIS depression measure will generate a referral to the study psychologist.

**Demographics:** The study is limited to adolescents experiencing subsyndromal depression. The demographic survey, administered at baseline, will collect data about each teen’s age, gender, race/ethnicity, years of education, and parental educational attainment.

**Qualitative measures:** We will collect two types of formal qualitative data: 1) Evaluation (focus) groups following each 8-week set of classes at the end of the last class; 2) Transcriptions of audio-recorded classes. The focus groups will address the following topics related to the teens’ experience with the programs, including:

- 1) Most memorable aspects of program (e.g. most favorite and least favorite aspects);
- 2) Whether they would recommend it to a friend;
- 3) Usefulness, challenges and recommended changes including in-class and out-of-class assignments;
- 4) Usefulness of the program for management of stress, mood, and well-being in daily life;
- 5) Tools that might help them maintain practices; and
- 6) Unfulfilled expectations of the program.

Each focus group will be audio-recorded and transcribed.

Table 2. Study measures		
MEASURE	CONSTRUCT	TIMING
Inclusion/Exclusion Criteria		
QIDS-SR	Depression screening	Pre-screening
Diagnostic Interview Schedule for Children (DISC-IV)	Screening for serious psychopathology	Screening visit
Primary Outcomes		
PROMIS Pediatric Depression Short Form v1.1	Incident major depression	Weekly from the beginning of the intervention
Secondary Outcomes		
Short Mood and Feelings Questionnaire (SMFQ-C)	Depression scores change	Visit 2, Visit 6, Visit 10, Visit 13, Visit 16
Brief Resiliency Scale (BRS)	Resiliency	Visit 2, Visit 6, Visit 10, Visit 13, Visit 16
Exploratory Mediating Measures		
Adolescent Cognitive Style Questionnaire (ASCSQ)	Cognitive Style	Visit 2, Visit 6, Visit 10, Visit 13, Visit 16

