- Individuals who develop severe distress during classes or who have a marked increase in symptoms (or reach the threshold for major depression) on the PROMIS pediatric depression short form will be referred immediately to the Study Psychologist, [name]. She will call the parent and assess the adolescent and provide the family with appropriate referrals.
- In the first class and periodically in other classes, instructors stress the importance of confidentiality, i.e., what is discussed in the room does not go beyond the room.

- Because of the inherent risk in this population, participants will be monitored at frequent intervals and will be followed for a sufficient period of time after the intervention to ensure stabilization of depressive symptoms. The educational programs to be tested are not commonly associated with increased risk of depression, but participants will be monitored weekly over 6 months for expected and unexpected AEs related to the programs.
- Participants may experience discomfort in answering some of the questionnaire questions or in making disclosures in the classes. Participants will be told that they may skip questions that they do not wish to answer and that disclosures in class are also entirely voluntary.

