### 7.3 Stopping Rules

The study will be stopped prior to its completion if: (1) the intervention is associated with adverse effects that call into question the safety of the intervention; (2) difficulty in study recruitment or retention will significantly impact the ability to evaluate the study endpoints; (3) any new information becomes available during the trial that necessitates stopping the trial; or (4) other situations occur that might warrant stopping the trial.

**Individual stopping rules.** If a participant scores above 12 on the combined parent and child SMFQ at any point in the study, s/he will be referred to the study psychologist ([name]) within 24 hours who will then contact the parent of the teen (within 24 hours) to inform the parent of the depression status of the teen. [name] will make an evaluation to determine if s/he can continue in the study and will refer the family for appropriate psychological care.

We have added a safety depression screening measure, the PROMIS pediatric depression scale, which will be administered weekly via REDCap. The Assessment Center at NIH provides a scoring algorithm with REDCap software, enabling use of the measure for safety monitoring. The Project Manager will monitor these measures weekly and will alert the team (including the Study Psychologist) to sharp increases in depressive symptoms and depressive symptoms meeting criteria for major depression (T score of 70). If the Study Psychologist confirms the development of major depression, the adolescent will be withdrawn from the study and referred for further care.

Additional reasons for withdrawal of a participant include:

1. The adolescent wishes to withdraw from the study;
2. Loss of study eligibility;
3. Intervening illness or injury making participation difficult;
4. The adolescent develops any condition that, in the opinion of the Study Psychologist would make continued participation unsafe.

In the unlikely event that a participant is unable to participate in a group setting, s/he may be withdrawn from the study.

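### PROMIS depression scores are available on submission but staff need only read them weekly, so a score at the referral trigger may go unread for days

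*Combined protocol and SAP*

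**What the plan says.** - **Scoring.** Under Expected Risks, the DSMP (Appendix IV) has teens complete PROMIS "through a survey interface on REDCap that provides immediate scoring".
- **Reading.** Protocol section 9.4.2: "The Project Manager or trained designee will monitor these measures weekly and will alert the team". DSMP section 7.3, Stopping Rules: "The Project Manager will monitor these measures weekly and will alert the team". DSMP Expected Risks treats the two mood measures differently in one sentence: "The project manager will monitor the PROMIS Depression short form scores weekly and scores on the Mood and Feelings Questionnaire (MFQ) after each administration".
- **Triggers.** Protocol section 7.1 sets two for PROMIS: a T score of 70, and a rise from baseline, for which "an increase of 3 standard deviations from the baseline score on the PROMIS depression measure will generate a referral". It does not say which standard deviation is meant.
- **Action.** DSMP Expected Risks says that teens with a marked rise, or at the major-depression threshold, "on the PROMIS pediatric depression short form will be referred immediately to the Study Psychologist". For the SMFQ, section 9.4.2 allows 24 hours for referral and a further 24 hours for the psychologist to reach the parent. It gives no such times for PROMIS.
- **Duration.** Section 5.1.3 says PROMIS "will be used as a safety measure once participants are in the 8-week course to assess any changes in depressive symptoms". The safety row of Table 2 and Appendix B.e also tie it to the 8-week program. The primary-outcome row of Table 2, section 5.3.2 and Table 3 carry it further.

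**The concern.** PROMIS was added as the frequent safety measure in teens selected because they are at risk of major depression. During the program the study questionnaires, including the SMFQ-C, come only at baseline and weeks 4 and 8 (section 10.3.3). PROMIS is therefore the only scheduled mood score in between. A weekly read gives up part of the benefit of a form that is scored on submission. The referral, the call to the parent and, where a high score is the only signal, the Study Psychologist's self-harm screen all wait for someone to open the record. This is a matter of safety procedure. No estimate, error rate or power figure depends on it.

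**Working it through.** The plan states no figure for this delay, so there is none to reproduce. The inputs are immediate scoring and immediate referral (DSMP Expected Risks), the weekly read (protocol 9.4.2; DSMP Expected Risks and 7.3), and the 24-hour parent-contact limit (9.4.2, written for the SMFQ). The completion day and the review day are not given.

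**1. Where the time goes.** The sequence is completion, score, read, referral, parent contact. The score takes no time, and the referral is immediate once the score is read. The only unbounded step before referral is from score to read.

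**2. Wait under the weekly read.** Let W be the time from completion to the next read.
- Fixed review day, interval R = 7 days: W lies between 0 and 7 days.
- If completion times were spread evenly over the week (an assumption), the mean is R/2 = 3.5 days and P(W > d) = 1 − d/R. That gives 1 − 1/7 = 86% waiting over 1 day, 1 − 2/7 = 71% over 2 days and 1 − 3/7 = 57% over 3 days.
- If everyone completes on one day and review falls on another fixed day, W is simply the offset between them. It could be hours.
- If weekly means once per calendar week on any day, one read can fall on the first day of a week and the next on the last day of the following week. The gap is then 7 + 6 = 13 days.

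**3. Wait under a 24-hour read.** Completion to read is at most 24 h, referral is immediate, and parent contact takes at most 24 h more: 24 + 24 = 48 h from completion. With an alert on submission that is acted on at once, it would be 0 + 24 = 24 h.

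**4. Why an alert at T of 70 is not enough.** Section 9.5.1 places T = 70 at 2 SD and T = 65 at 1.5 SD above the population mean, so one population SD is (70 − 65)/(2 − 1.5) = 10 points. A rise of 3 SD that stays below 70 requires a baseline under 70 − 3 SD.
- If section 7.1 means the population SD: 70 − 30 = 40.
- If it means a smaller SD, say 5 points (an assumption): 70 − 15 = 55.

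The alert would miss these teens, and on the second reading the group could be sizeable.

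**5. Forms under the rule.** Table 3 gives 1 + 3 + 1 + 3 + 1 = 9 forms over weeks 0 to 8, or 8 if counted from week 1. For 80 teens that is 640 to 720 planned forms. This counts forms subject to the rule. It does not count delayed forms or forms at the trigger.

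**The case against.** The strongest reply is that a weekly read of a weekly form naturally means one read per form, soon after it arrives. The SMFQ comes at irregular visits and so needs event-based wording, whereas PROMIS does not. This reading is possible, and the contrast between the two measures should not be pressed, because the SMFQ read is not given in hours either. But neither the completion day nor the review day is fixed, so nothing requires the short delay.

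A reader might infer that the plan contradicts itself by promising immediate referral after a weekly read. It does not: the referral can run from detection, and after the read the rule is strict.

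A reader might also infer that a teen in crisis is unprotected until the read. The documents do not support that. PROMIS asks about the past 7 days and has no self-harm item. Someone with mental-health training attends every class, severe distress in class triggers referral without any PROMIS score, and families and staff can reach the Study Psychologist directly. These channels handle much of the acute risk, but none sets a time for reading PROMIS. Section 7 also counts the daily diary as safety monitoring, but the form in Appendix B.g asks only about practice. The post-completion check in section 10.3.3 concerns completeness of the visit questionnaires.

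Two further points stand. A Manual of Procedures, cited in DSMP section 8 but not supplied, may already set a read time. And the past tense in section 9.5.1 and the version 1.1 revision note suggests that collection may be over.

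**Conclusion.** The concern holds in a limited form. The plan requires only a weekly read of a score that is available at once, and does not tie the read to completion. A score at either trigger may go unread for days: roughly 0 to 7 with a fixed review day, less if reads follow completion, up to about 13 if the day floats. Seven days is neither a typical delay nor a secure ceiling, and the 3.5-day mean rests on an even spread of completion times that the documents do not give.

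The number of teens affected cannot be stated, since section 9.5.1 itself allows that few may reach T = 70. The finding is firm for the 8-week program. It extends to the continuation phase only if weekly PROMIS continues there, on which the documents conflict. The change is worth making because it is cheap and safer.

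**What to change.** In protocol section 9.4.2 and the matching DSMP text (Expected Risks and section 7.3):

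1. Require each PROMIS form to be read within 24 hours of completion against both triggers in section 7.1: T of 70 or more, and the 3 SD rise from baseline. State which SD is meant.
2. Optionally add a REDCap alert on submission at T of 70 or more. The documents describe REDCap scoring but no alert function, so this depends on availability. It should not replace the 24-hour check of the 3 SD trigger.
3. Keep the DSMP's immediate referral, running from the read or alert. Do not substitute the SMFQ's looser 24-hour referral limit.
4. Apply to PROMIS the 24-hour parent-contact limit already used for the SMFQ.
5. Keep the weekly check for missed forms.

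If the Manual of Procedures already sets a read time, move it into these sections. If PROMIS collection has ended, carry the rule into the planned larger trial.

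The cost is a few lines of text and a daily look at scores REDCap already computes. Staff already collect adherence data twice weekly (DSMP section 7.1.2). The downside is occasional weekend or out-of-hours reads, for which a designee must be named.
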